6b Choice of Comparator: Control participants will receive placebo capsules containing 288 mg of rice protein (California Natural Products, Lathrop, CA), 109.3 mg microcrystalline cellulose (Stauber USA, Fullerton, CA), 4.3 mg Aerosil® 200 fumed silica (Vivion Inc., San Carlos, CA), and 4.3 mg magnesium stearate (Nitika Pharmaceutical Specialties, Maharashtra, India), and formulated into a capsule by Metagenics, Inc. (Gig Harbor, WA).

7 Objectives

A methodological limitation of assessing the efficacy of CD treatments is that the gut microbiome of CD subjects is highly personalized in terms of state and dynamics. By correlating time-resolved fluctuations in the gut microbiome of CD subjects with their concomitant changes in the profile of XN metabolites, BA profiles, and other markers of gut microbiome-associated biochemical activity as well as with established surrogate end-points of the disease, we hypothesize:

1) XN at the given dose will be safe and tolerable in adults with active CD;

2) XN will improve biomarkers and improve the Crohn's Disease Activity Index (CDAI) an activity index of CD activity;

3) We can identify a biological signature(s) of XN through its metabolic byproducts in blood, urine, and stool as well as its effect on bile acid reabsorption; and

4) Specific biological signature(s) of XN exposure will uniquely contribute to changes in CD-associated disease activity indices.

To test these hypotheses and generate a conceptual model, we define four Specific Aims:

Protocol

- Aim 1. Determine the clinical safety and tolerability of xanthohumol in adults diagnosed with CD. We will determine the safety and tolerability of xanthohumol in adults diagnosed with CD over 8 weeks in a Phase 2 trial. The primary hypothesis is that in the XN arm, the number of participants with an adverse event or abnormal lab value will not be more than 50% higher than the number in the placebo group.
- Aim 2. Assess changes in levels of inflammation and symptom severity related to CD.

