A sample size of 12 per group provides 80% power to detect a 50% difference in proportions of participants between groups by chi2 test experiencing a laboratory abnormality or adverse event at a significance threshold of α =0.05. In addition, based on our preliminary trial data for change in TNF- α , and applying a 2-sided t-test of means, n=24 allows for n=12 per arm and provides >90% power, at a significance threshold α =0.05, to detect a mean change of -0.5 =/- 0.25 pg/ml in XN-treated participants with CD, based on an estimated mean change of 0.1 +/- 0.25 pg/ml from placebo. Will we randomize up to 32 participants to allow for attrition up to 25% [resulting in a final sample of at least n=24/arm.

Based on our preliminary trial data for change in TNF- α , and applying a 2-sided t-test of means, n=24 allows for n=12 per arm and provides >90% power, at a significance threshold α =0.05, to detect a mean change of -0.5 =/- 0.25 pg/ml in XN-treated participants with CD, based on an estimated mean change of 0.1 +/- 0.25 pg/ml from placebo. Will we randomize up to 32 participants to allow for attrition up to 25% [though we had <10% attrition in our previous trial in this population] resulting in a final sample of at least n=24/arm.

15 Recruitment

Participants will be recruited from the region via posted fliers and the NUNM clinic via posted fliers and IRB-approved mailings to current patients. Members of the study team will present information about study participation to CD support and community groups and set out flyers for attendees to pick up. In addition, we will use Craigslist and social media (i.e. Facebook and Instagram) as well as the NUNM weekly newsletter. Candidates from the community would

simply respond to a dedicated study telephone line or email, and express their interest, and are then contacted by a Study Coordinator.

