Determining differential abundance between treatments: High-level exploratory analyses will be performed through metrics such as alpha and beta diversity and ordination techniques. Further, differential abundance analysis for 16S and metagenomics data will be conducted through negative binomial models, with specifications to deal with inflation of zero counts, such as those implemented in statistical R packages edgeR and DESeq2 or through a compositional Bayesian data analysis approach, such as the approach implemented in the R package ALDEx2.²⁰⁻²² Exploratory data analysis will first be done to evaluate which modeling technique is appropriate for the data generated based on assumptions made by each modeling approach. For MS-based omics data, we use a suite of robust statistical approaches for: 1) processing the data to identify outliers, and 2) identifying statistically different proteins and metabolites between comparative samples. As a first step to statistical testing, we use the Statistical Procedure for the Analysis of molecular abundance Normalization Strategies (SPANS) approach to simultaneously evaluate several MS-based omics data set normalization strategies to determine the most appropriate normalization factor in the context of the experimental design.²³⁻²⁶ For individual data streams, there are several strategies for identifying molecular features that statistically classify patients, depending on the structure of the data and the phenotype data being used for classification. For the determination of statistically relevant features, if the features follow the standard normal distribution, then we utilize standard ANOVA methods; otherwise, a non-parametric version, such as Kruskal-Wallis or sum-rank test, can be utilized.²⁷

Longitudinal regression modeling:

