provides genome-centric resolution by integrating genome binning. The full ATLAS protocol is developed and maintained as open-source software on GitHub and is implemented in Snakemake for modular, flexible, and reproducible workflows. Individual protein sequence databases will be created based on a combined metagenome that will serve as references for paired metaproteome analysis. To complement these assemblies and produce as comprehensive an assessment of microbiome structure and functional capacity as possible, we will also conduct analyses at the level of individual, unassembled reads. Specifically, we will analyze quality-controlled metagenomes using MetaPhlan2 to measure the abundance of specific microbial taxa in each metagenome.⁴¹ We will also use ShotMAP to assign reads into KEGG Orthology groups based on homology.³³ Briefly, ShotMAP predicts coding sequences from unassembled metagenomic data using Prodigal and applies RAPsearch or DIAMOND to rapidly identify reads that show evidence of homology to KEGG Orthology groups. Our prior statistical simulations surrounding this technique highlight its accuracy and our prior applications of these tools resolved taxa and microbiome metabolic modules that predict immune activation in mouse models of IBD and flare-ups in IBD patients.^{28,33}

20b Subgroup and/or adjusted analyses.

No subgroup analyses are planned. If significant differences in disease severity (CDAI-measured) become evident between XN- and placebo-treated groups, ANCOVA will be performed for all tests of mean differences (i.e., pro-inflammatory cytokine, gut permeability and endotoxemia-related parameters), adjusting for baseline CDAI score between groups.

20c Methods for imputation and/or consideration of protocol non-adherence.

To evaluate the statistical relevance of missing data, for example when the data is absent in the control group and present in the treatment group, we will utilize a G-test.²⁵ However, with multiple comparisons comes the problem of increased likelihood of a significant result by random chance. To counter this problem, we use either the Dunn-Sidak or Bonferroni correction to adjust p-values.⁴² If the data have a linear relationship, then we use partial least squares discriminant analysis (PLS-DA) and rank the molecules by p-value in a pair-wise comparison to the control group.^{43,44}

Monitoring

21a Data monitoring

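### The protocol's only multiplicity rule is family-wise with undefined scope; applied to untargeted omics features at 12 per arm, it leaves low power per feature, and false-discovery-rate control suits these aims better

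*Protocol*

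**What the plan says.** Section 20c, on imputation and non-adherence, opens with missing data: "for example when the data is absent in the control group and present in the treatment group, we will utilize a G-test". It then notes that many comparisons raise the chance of a false positive and says "we use either the Dunn-Sidak or Bonferroni correction to adjust p-values". The next sentence turns to PLS-DA and a ranking of molecules by p-value. No family, family size or list of analyses is given, and no false-discovery-rate method is named anywhere in the protocol.

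The feature-wise testing itself is described in section 20a, under differential abundance. It covers 16S and metagenomic data and, for mass-spectrometry data, "identifying statistically different proteins and metabolites between comparative samples". Section 20a has no multiplicity rule and does not refer to 20c.

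The aim served is hypothesis 3 in section 7: "We can identify a biological signature(s) of XN through its metabolic byproducts in blood, urine, and stool", together with the effect on bile acid reabsorption. Hypothesis 4 relates such signatures to disease activity. Table 1 in section 12 ranks XN metabolites and bile acids as tertiary outcomes and lipidomics as exploratory.

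**The concern.** A signature is a list of features. For a list, the useful guarantee is that only a known share of entries is false. Dunn-Sidak and Bonferroni instead guard against even one false entry, and the price rises with the number of features. In a small trial with untargeted panels that price can be most of the true features.

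The unclear scope adds to this. If 20c governs the 20a tests, the omics lists may be much shorter than the data could support. If 20c governs only the G-test, the 20a tests have no multiplicity rule in the protocol. The text needs an edit in either case.

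**Working it through.** **Sample size.** Section 14 says "n=24 allows for n=12 per arm and provides >90% power" and then "Will we randomize up to 32 participants to allow for attrition up to 25" per cent. 32 × 0.75 = 24 in total, so 12 per arm. The same section's "resulting in a final sample of at least n=24/arm" does not follow from that arithmetic; 12 per arm is used here, with 16 per arm as the no-attrition case.

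**The plan's own power figure.** Section 14 takes TNF-α changes of −0.5 and +0.1 with SD 0.25, "applying a 2-sided t-test of means", α = 0.05. Then d = 0.6/0.25 = 2.4. Noncentral-t power with 22 degrees of freedom and noncentrality d√(n/2) = 2.4 × √6 = 5.88 is 99.99%. The stated figure of more than 90% holds. The protocol gives no power figure for any omics feature.

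**Power per feature under Bonferroni.** The same formula with α = 0.05/m, where m is the number of features. Both m and d are assumptions, except m = 6 (XN plus five metabolites named in section 12) and d = 2.4 (the TNF-α effect above).

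| m, at 12 per arm | d = 0.8 | d = 1.2 | d = 2.0 | d = 2.4 | d for 80% power |
|---|---|---|---|---|---|
| 1 | 47% | 80% | 99.7% | 99.99% | 1.20 |
| 6 | 20% | 53% | 97% | 99.7% | 1.55 |
| 100 | 4% | 18% | 77% | 94% | 2.05 |
| 1,000 | 0.8% | 5% | 48% | 77% | 2.46 |

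At 5,000 features, d = 1.2 gives 2% and 80% power needs d = 2.75. Dunn-Sidak, with α = 1 − 0.95^(1/m), changes power at d = 1.2 by less than 0.4 percentage points. With 16 per arm and 1,000 features, d = 1.2 gives 13% and 80% power needs d = 2.01.

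**Presence or absence.** For the G-test, 0 of 12 against 12 of 12 gives G = 33.3 and p = 8 × 10⁻⁹. The Bonferroni threshold at 10,000 features is 0.05/10,000 = 5 × 10⁻⁶, so complete separation passes easily.

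**Bonferroni against Benjamini-Hochberg (BH).** Simulation with 1,000 independent normal features, 12 per arm, two-sample t-tests, both methods at 5%. Entries are the share of truly changed features that are found.

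| d | Features changed | Bonferroni | BH |
|---|---|---|---|
| 0.8 | 10% | about 1% | about 2% |
| 1.2 | 1% to 20% | 5% | 7% to 44% |
| 1.5 | 1% | 15–16% | 26–28% |
| 1.5 | 10% | 15% | 65% |

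In the last row about 4% of the BH discoveries are false. At the same level BH rejects everything that Bonferroni rejects, so it is never less powerful.

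**The case against.** The strongest objection is about scope. The rule sits in the missing-data section, right after the G-test, and 20a does not refer to it. A reader might infer that the plan controls the family-wise error across all taxa, genes, metabolites and lipids; the protocol does not say that. The context does point to omics data, since the G-test is cited to a mass-spectrometry proteomics paper and the next sentence ranks molecules. The reach into 20a remains conditional, and a SAP may define the families. What a SAP need not supply is the method, because the protocol has already named it.

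A reader might also infer that hypotheses 3 and 4 could not be answered. That is not supported:
- The six targeted analytes keep 53% to 97% power at d = 1.2 to 2.0.
- Compounds present only on XN pass any such threshold.
- Section 20a plans longitudinal models, acknowledges that they may lack power, and offers elastic net as a better-powered route. Elastic net does not use corrected p-values, and a Bonferroni factor leaves the PLS-DA ranking unchanged.
- Even Bonferroni would not return an empty list in the d = 1.5 case: 15% of 100 changed features is about 15.

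Nor does false-discovery-rate control always rescue the analysis. At d = 0.8, or with few changed features, it adds little, because the sample is the limit.

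Finally, family-wise control is a valid, conservative method. That stands. The point is that it fits a discovery list poorly, not that it is an error.

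**Conclusion.** The point holds in conditional form, as a low-cost improvement. The protocol's one multiplicity rule is family-wise and its scope is undefined. If it is applied to untargeted feature-wise tests at 12 per arm, power per feature is about 1% to 18% for d between 0.8 and 1.2 and 100 to 1,000 features. Benjamini-Hochberg would recover more, by an amount ranging from negligible to several-fold. These sizes rest on assumed feature counts, effect sizes and shares of changed features, and on independent normal features compared by t-tests. The planned count models and repeated-measures models would give different values, and correlation between features would change the spread of results. The safety and TNF-α calculations of section 14 are not affected.

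**What to change.** State the rule in section 20a, where the tests are described, and limit 20c to missing data. For untargeted feature-wise tests (taxa, genes, metabolites, lipids, and the G-test across molecules), replace Dunn-Sidak or Bonferroni with Benjamini-Hochberg at a stated level, for example 5% or 10%, within each data type. Report adjusted values for all features, not only those that pass. Family-wise control may stay for the small targeted set of XN and its named metabolites.

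This costs a sentence or two and needs no new data. The downside is that a small, controlled share of the listed features is expected to be false, which is acceptable for tertiary and exploratory aims if the report says so.

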We aim to extend our preliminary findings related to potential application of XN as a therapeutic by testing its effects in a sample of human adults with CD. We will recruit 32 participants with CD, and randomize them to either 24 mg of XN plus rice protein, or a rice protein placebo for 8 weeks. The study drug will be identical to the preparation used in the Phase 1 trial that preceded this Phase 2 protocol, i.e., XN will be administered as 24 mg of a 99+% pure raw material provided by Hopsteiner USA (NY) combined with 288 mg of rice protein (California Natural Products, Lathrop, CA), 109.3 mg microcrystalline cellulose (Stauber USA, Fullerton, CA), 4.3 mg Aerosil®

Protocol

200 fumed silica (Vivion Inc., San Carlos, CA), and 4.3 mg magnesium stearate (Nitika Pharmaceutical Specialties, Maharashtra, India), and formulated into a capsule by Metagenics, Inc. (Gig Harbor, WA). XN has been combined with a rice protein carrier due to improved bioavailability.⁹

Our *primary working hypothesis* is that XN at the given dose will be safe and tolerable in adults with active CD. We will test this hypothesis by collecting blood samples at screening, baseline, and every two weeks to monitor changes in laboratory values including liver enzymes, renal function markers, and hematological markers. We anticipate very low frequency of treatment discontinuation due to adverse effects.

Our *working hypotheses* of Aims 2, 3, and the Exploratory Aim are that XN and its microbiotaderived metabolites may reduce inflammation and reduce biomarkers of barrier permeability in the inflamed gut. In order to test this hypothesis, we will collect blood, urine, and stool samples at baseline and every two weeks to monitor gut microbiome profiles and measure XN metabolite profiles. We will also measure fecal metabolome (including bile acid profiles) and lipidome profiles, as well as established fecal and plasma indicators of IBD severity, including fecal calprotectin and C-reactive protein. Because the actions of XN and its metabolites target specific abnormalities in CD, we hypothesize that the proposed studies will deliver a mechanism-based biological signature of XN exposure and its effect on CD mitigation.

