Because Black/African Americans are under-represented in the Portland metro area, we will specifically target recruitment strategies to reach Black/African Americans in the region.

No NIH-defined children will be enrolled.

Assignment of interventions (for controlled trials) Allocation

16a Sequence generation

Randomization will occur in up to 8 blocks of 4 based on biological sex. Initial randomization series will be generated using readily available random sequence generators designed to do so such as Randomization.com, which allows for block randomization.

16 b Allocation Concealment mechanism

Envelopes will be opaque and signed across the seal. The randomization "code" will be kept in a password protected folder that will only be accessible by NUNM's Information Technology staff.

16c Implementation

Masking will be accomplished by: using trained staff not involved in trial operations to: 1. Produce the "code" (e.g., X2=XN and Y1=Placebo); 2. Label XN and placebo bottles generically as "X2" and "Y1"; 3. Generating the blocked randomization sequence using Randomization.com; 4. Create 32 sequentially-numbered, sealed envelopes that contain the random group assignments. Upon confirmation of eligibility and interest, Study Coordinators involved with trial operations will then open the next sequential envelope in the stack at the time of randomization, the envelope number will be recorded, and allocation disclosed to both participant and coordinator at that time as simply "X2" or "Y1", indicating which bottles will be dispensed.

17a Blinding (masking)

Triple-masked without PI, Study Coordinator, or Participant knowing participants' allocation assignment.

17b Un-blinding/masking

Un-blinding is permissible if the Data Safety Monitoring Board requires it upon review and in the case of a Serious Adverse Event (SAE).

Data collection, management, and analysis

18a Data collection methods

1. Adverse Events Report Form

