A Data Safety and Monitoring Board (DSMB) independent of the study team will be created for the proposed trial and will consist of: a clinical investigator with IBD experience, a clinician with IBD practice experience, a biostatistician, and at least one other experienced clinical researcher/trialist. The DSMP will review all AE reports according to IRB policy, monthly reports of recruitment, retention and overall study progress; and attend quarterly meetings. Protocol amendments can be suggested by members of the independent monitoring committee at any time, and additional meetings of the DSMB can be called by any member at any time. The PI and study coordinator will also participate in quarterly meetings with the committee to provide additional information and/or clarify reports.

21b This study will be stopped prior to its completion if the intervention is associated with adverse effects that call into question the safety of the intervention, if any new information becomes

Protocol

available during the trial that necessitates stopping the trial; or if other situations occur that might warrant stopping the trial. The ultimate decision to stop the trial may be made by the DSMB, NCCIH, and/or the FDA.

The trial will be halted if >25% of the total sample experience moderate or greater AEs or laboratory abnormalities requiring them to withdraw.

The DSMB will provide a final recommendation to the PI to halt the study or amend the study protocol, and will develop a response plan, in consultation with the NUNM IRB and the NCCIH Program Officer.

If immediate changes are required for participant safety, enrollment and other study activities will not continue until the modifications/amendment is approved by the IRB.

22 Harms

Adverse Event Monitoring and Reporting

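### The 25% halting limit pools both arms: with 32 participants it needs 9 withdrawals, so 8/16 on XN against 0/16 on placebo would not trigger it

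*Protocol*

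**What the plan says.** Protocol section 21b states: "The trial will be halted if >25% of the total sample experience moderate or greater AEs or laboratory abnormalities requiring them to withdraw". No count by arm and no comparison between arms is attached to this limit. The same section also has a qualitative ground, under which the study stops "if the intervention is associated with adverse effects that call into question the safety of the intervention", and leaves the final decision to the DSMB, NCCIH and/or the FDA. Under 17b, "Un-blinding is permissible if the Data Safety Monitoring Board requires it upon review".

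The primary hypothesis in section 7 (Aim 1) is comparative: in the XN arm, "the number of participants with an adverse event or abnormal lab value will not be more than 50% higher" than in the placebo group.

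Section 14 plans up to 32 randomised participants. Section 16a randomises them in up to 8 blocks of 4. On discontinuation, section 6a says: "We anticipate very low frequency of treatment discontinuation due to adverse effects".

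**The concern.** A count pooled over both arms carries no information about the contrast that the primary aim addresses. Four withdrawals in each arm and eight on XN with none on placebo give the same 8/32. Placebo participants enlarge the denominator but, if the harm comes from XN, add little to the numerator. Harm confined to XN therefore has to be large before the stated number is reached, and until then stopping depends on the DSMB's judgement alone.

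The limit also leaves its denominator open. The total sample could be the 32 planned or the participants enrolled so far, and two careful readers could disagree on whether the trial must halt.

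**Working it through.** **Inputs from the protocol.** The limit is strictly more than 25% of the total sample (21b). The maximum sample is 32 (sections 6a and 14). Section 14 reaches 32 from 24 completers and 25% attrition: 24/(1 − 0.25) = 32, which reproduces. Sixteen per arm is inferred, not stated: section 14 puts 12 of 24 in each arm, and 8 full blocks of 4 give 16 and 16. Unfilled blocks within a sex could shift this slightly.

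**Count needed.** 0.25 × 32 = 8. The inequality is strict, so 8/32 = 25.0% does not trigger and 9/32 = 28.1% does. If all 9 are on XN, that is 9/16 = 56%.

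**The silent case.** 8/16 on XN against 0/16 on placebo gives 8/32 = 25.0%, so the limit is not reached. The two-sided Fisher exact p is 0.0024. A split of 5/16 against 0/16 already gives p = 0.043.

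**How often each limit is reached by trial end.** The protocol gives no withdrawal rates, so those below are assumptions. Let X ~ Bin(16, pX) be withdrawals on XN and Y ~ Bin(16, pP) those on placebo. The pooled limit is reached with probability P(X + Y ≥ 9). The same percentage within an arm needs 5 of 16 (4/16 is exactly 25%), with probability P(X ≥ 5) for the XN arm.

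| XN rate | Pooled, placebo 0% | Pooled, placebo 5% | Pooled, placebo 10% | XN arm, 5 or more of 16 |
|---|---|---|---|---|
| 30% | 0.026 | 0.081 | 0.167 | 0.550 |
| 40% | 0.142 | 0.267 | 0.404 | 0.833 |
| 50% | 0.402 | 0.551 | 0.677 | 0.962 |
| 60% | 0.716 | 0.813 | 0.882 | 0.995 |

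**The other reading of the denominator.** If it means enrolled to date, fewer withdrawals suffice early on (5 of 16, 7 of 24). In 100,000 simulated trials with blocks of 4, immediate outcomes and a check after every participant from the 8th or the 16th, and placebo again at 0-10%, the pooled limit is reached in 16-53% of trials at 30% on XN and 41-75% at 40%. That is more sensitive than a denominator of 32. At both rates it stays below the fixed count of 5 of 16 (55% and 83%).

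**False pauses with 5 of 16 in either arm.** If both arms share the rate p, the chance is 1 − P(Bin(16, p) ≤ 4)²: 0.2% at 5%, 3.4% at 10%, 15% at 15% and 36% at 20%. A running by-arm percentage checked after every participant from the 8th or 16th would instead give 3-10% at 5% and 19-32% at 10%. A fixed count does not inflate with repeated looks, which is why it is preferable.

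**The case against.** The strongest defence is that the pooled number is not the only safeguard. The qualitative ground in 21b is worded as mandatory, concerns the intervention itself, and would cover 8 against 0. The DSMB includes a biostatistician, reviews all AE reports, adjudicates relatedness, can be convened by any member at any time, and can require unblinding. Section 11b also withdraws individuals with attributable moderately severe gastrointestinal events or critical laboratory values. All of this stands, and it would be wrong to say that nothing could stop the trial at 8 against 0. But none of it sets a by-arm limit, and the protocol does not say that the DSMB's reports are split by arm. A DSMB charter might; it is not among the documents.

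A second objection is that the assumed XN rates of 30-60% lie far from what the protocol expects. Section 6a reports no discontinuations due to AEs in Phase 1, and section 14 cites under 10% attrition in an earlier trial in this population. At lower XN rates a limit of 5 of 16 in that arm is itself seldom reached: 1.7% at 10% and 20% at 20%. That is fair, but a halting limit exists for the case where expectations prove wrong.

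A third is that the halting limit counts withdrawals while Aim 1 counts any AE or abnormal laboratory value, so the two need not match. They need not use the same event, but a safety limit in a placebo-controlled trial should still be able to distinguish the arms.

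Finally, the words about withdrawal could be read as applying to laboratory abnormalities only. Moderate AEs without withdrawal would then count and the limit would be more sensitive, though still pooled.

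**Conclusion.** The concern holds. The protocol's only numerical halting rule cannot tell 4 against 4 from 8 against 0. On a denominator of 32, with 16 per arm, it needs 9 withdrawals and would be missed more often than not at 40% withdrawal on XN (reached in 14-40% of trials, against 83% for 5 of 16 in that arm). These probabilities rest on assumed withdrawal rates and on complete blocks; the count of 9 and the 8-against-0 example depend only on the denominator and the arm sizes. If the denominator is enrolled to date, the shortfall is smaller but remains. This is a design weakness that should be corrected, not an error that invalidates the trial, because the DSMB keeps its discretion to stop.

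**What to change.** In 21b, keep the pooled limit and state its denominator (32 planned, or participants dosed to date). Add one sentence: if 5 or more participants in either coded arm (X2 or Y1; more than 25% of the 16 planned) withdraw for a moderate or greater AE or a laboratory abnormality, enrolment pauses for DSMB review. Use the fixed count of 5, not a running by-arm percentage. Clusters that appear before the fifth withdrawal stay with the existing qualitative clause.

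Section 16c already labels the bottles by code, so the DSMB biostatistician can keep the count by code and the investigators stay masked. As the PI and coordinator join the quarterly meetings, the by-arm count should not be shown there.

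The cost is one sentence in 21b or the DSMB charter, one coded count per quarterly report, and the false-pause risk: 3.4% if both arms have 10% withdrawal, rising to 36% at 20%, a rate well above what the protocol expects. The consequence is a pause for review, not termination.
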